#### 6.2. Clinical Laboratory Tests

All clinical laboratory reports will be displayed for the participants included in the safety analysis set. The clinical laboratory parameters to be evaluated by the central laboratory include but are not limited to:

- Hematology: Complete Blood Count (CBC) with differential, platelets, and hemoglobin.
- Chemistry: albumin, alkaline phosphatase, alanine aminotransferase, aspartate aminotransferase, total bilirubin, blood urea nitrogen/urea, calcium, chloride, creatinine, GGT, glucose, potassium, total protein, sodium, bicarbonate.

Box plots of laboratory measurements and change from baseline will be provided for the selected laboratory measurement.

Applicable laboratory results will be graded according to National Cancer Institute's Common Terminology Criteria for Adverse Events (NCI-CTCAE version 5.0). The worst NCI-CTCAE will be summarized by treatment group.

A listing of participants with 1 or more NCI-CTCAE toxicity grade  $\geq 2$  in hematology and clinical chemistry laboratory measurements will be provided

## 6.3. Vital Signs and Physical Examination Findings

Vital signs including pulse, blood pressure (systolic and diastolic), body temperature, peripheral blood oxygen saturation (SpO2) and respiratory rate will be measured at visits (pre-injection and

post-injection) as per the schedule of activities in the protocol. Descriptive statistics of the observed value and change from baseline of the vital signs will be summarized by treatment group over time.

Physical exam findings will not be analyzed. When physical exam findings are captured as AEs, those will be included in the analyses of AEs.

## 7. PHARMACOKINETICS/PHARMACODYNAMICS

## 7.1. Pharmacokinetics

All PK analyses will be based on the PK analysis set (Section 2.4.3). Participants will be analyzed according to the randomized treatment groups they were assigned to, regardless of the treatments they actually received. Unless otherwise specified, tabular summaries of PK for key study periods are in general presented as following:

#### Summaries through Week 16:

PK data through Week 16 will be summarized by treatment groups

- Bermekimab 400 mg q2w
- Bermekimab 400 mg qw

## Summaries through Week 36:

PK data through Week 36 will be summarized by treatment groups including

- Placebo  $\rightarrow$  Bermekimab 400 mg qw
- Bermekimab 400 mg q2w
- Bermekimab 400 mg qw

## 7.1.1. Bermekimab Concentrations

Blood samples for measuring bermekimab concentrations will be collected from all participants at the specified visits as shown in the schedule of activities in the protocol. Samples will also be collected at the final visit from participants who terminate study participation early. Samples must be collected before study agent administration at visits when a study agent administration is scheduled.

Bermekimab concentrations will be summarized using descriptive statistics, including n, arithmetic mean, SD, coefficient of variation (%CV), median, interquartile range, range (minimum and maximum), by treatment group at each PK sampling time where appropriate. PK data may be displayed graphically. The following analyses will be performed as appropriate:

- Summary of bermekimab concentrations at each visit by treatment group.
- Proportion of participants without detectable bermekimab concentration (below the lower limit of quantification) at each visit by treatment group.

- Summary of bermekimab concentrations at each visit by treatment group and baseline body weight (quartiles). Other covariates may also be applied.
- Summary of bermekimab concentrations at each visit by treatment group and baseline Hurley stage status .
- Summary of bermekimab concentrations at each visit by treatment group and prior biologic use status.
- Plot of mean (SD) bermekimab concentrations over time by treatment group.
- Plot of median (IQ) bermekimab concentrations over time by treatment group.

## 7.1.1.1. Data Handling Rules

Unless otherwise specified, the following data handling rules will apply to PK analyses:

- Participants will be analyzed according to the treatment groups that they actually received.
- All concentration summaries for a particular timepoint will include data obtained from treated participants at the timepoint of interest without imputing any missing data.
- A concentration not quantifiable (below the lower limit of quantification) will be treated as 0 in the summary statistics and shown as the lower limit of quantification (< LLOQ) in the data listings.
- The data from a participant who meets 1 of the following dosing deviation criteria (if applicable) will be excluded from the by-visit data analyses from that point onwards:
- Discontinue bermekimab administrations.
- Skipped a bermekimab administration.
- Received an incomplete/ incorrect dose (if applicable).
- Received an incorrect study agent (if applicable).
- Received an additional bermekimab dose.

In addition, if a participant has an administration outside of dosing windows (Table 2), the concentration data collected at and after that visit will be excluded from the by-visit data analyses. Additional exclusions for incongruous PK data to be implemented based on Janssen SOP-07948. All participants and samples excluded from the analysis will be clearly documented in the Clinical Study Report.

Visit	Window
Week 0 through Week 32	$\pm$ 3 days from scheduled visit day
Final Safety and Efficacy Follow-up visit	$\pm$ 7 days from scheduled visit day

Table 2:	Dosing Window
----------	---------------

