## 1.2. Trial Design

This is a randomized, double-blind, placebo-controlled study to further establish the efficacy and safety and explore dose effects for bermekimab monotherapy in adults with moderate-to-severe HS. It is anticipated that approximately 50% of patients enrolled will have failed prior targeted biologic therapy(ies) and approximately 50% will be naïve to these forms of biologic therapy in each arm. Patients will be assessed for study eligibility at the initial screening visit after providing informed consent. Thirty days are allowed in the screening window to complete all screening procedures and randomize the participant. During the screening period, certain treatments will be washed out, as applicable, according to eligibility requirements. Patients who fail initially may be re-screened once based on the investigator discretion but only if inclusion criteria are met at time of re-screening.

The study is approximately 40 weeks (30-day screening period, 32-week treatment period and a 4-week follow-up period) for all participants.

A diagram of the study flow (Figure 1) is provided below. Approximately 150 patients who meet eligibility criteria at screening will be randomized in a 1:1:1 fashion to one of three treatment arms:

**Bermekimab 400 mg SC (qw) (Treatment Arm 1)**: 800 mg loading dose of bermekimab (2 x 400 mg SC injections) at weeks 0 and 1 followed by weekly (qw) subcutaneous (SC) injections of 400 mg bermekimab through week 31

**Bermekimab 400 mg SC (q2w) (Treatment Arm 2)**: 800 mg loading dose of bermekimab (2 x 400 mg SC injections) at weeks 0 and 1 followed by subcutaneous (SC) injections of 400 mg bermekimab every other week (q2w) alternating with matching placebo q2w through week 31.

**Placebo (Treatment Arm 3)**: 4mL loading dose of placebo (2 x 2mL SC injections) at weeks 0 and 1 followed by weekly placebo injections from week 2 through week 15. Patients in Arm 3 will begin to receive weekly (qw) blinded subcutaneous (SC) injections of 400 mg bermekimab beginning at week 16 through week 31.

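### The SAP's off-window PK exclusion is permanent and, as worded, can be triggered by a placebo injection; the SAP also gives two opposite treatment-assignment rules for PK.

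*SAP*

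**What the plan says.** SAP 7.1.1.1 sets the handling rules for bermekimab concentrations. A list of five dosing deviations removes a participant from the by-visit analyses from that point on. Three of the five name the active drug: discontinuation, an additional dose, and "Skipped a bermekimab administration". A further rule follows the list: "if a participant has an administration outside of dosing windows (Table 2), the concentration data collected at and after that visit will be excluded", again from the by-visit analyses. Table 2 sets the window at 3 days either side of the scheduled day for "Week 0 through Week 32" and does not separate active from placebo injections. Neither the list nor the window rule has a re-entry provision.

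Under SAP 1.2 and 1.5.2 every arm is injected weekly through Week 31. From Week 2, Arm 2 receives bermekimab "every other week (q2w) alternating with matching placebo q2w through week 31". Arm 3 receives only placebo until its first bermekimab dose at Week 16.

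On treatment assignment, SAP 7.1 states: "Participants will be analyzed according to the randomized treatment groups they were assigned to, regardless of the treatments they actually received". SAP 7.1.1.1 states: "Participants will be analyzed according to the treatment groups that they actually received".

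**The concern.** The timing of a placebo injection cannot change a bermekimab concentration. A rule that lets a late placebo injection remove later samples therefore loses valid data for nothing. Arm 3 is the sharpest case: a late injection in, say, Week 5 would remove the participant from every post-crossover by-visit summary, although no bermekimab had yet been given.

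Because the exclusion is permanent, the retained group can only shrink, and it shrinks most where sampling is sparse. After Week 16 the protocol calendars schedule PK samples only at Weeks 24, 32 and 36. The Week 16 sample is taken before dosing, so those three are Arm 3's only scheduled samples on bermekimab. Late visits are foreseeable, since the COVID-19 appendix allows visits to be delayed until on-site attendance resumes.

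PK is a protocol secondary endpoint, and SAP 2.4 uses the Week 16 lock, which includes PK data, to plan later development. The two assignment rules are a separate defect: a programmer cannot follow both.

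**Working it through.** **Wording.** The window rule refers to any administration. The nearby criteria for discontinued, skipped and additional doses specify bermekimab. Table 2 covers all dosing weeks without distinction. The plain reading is that any injection, active or placebo, triggers the exclusion, although the SAP never says so in terms.

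**Which injections are placebo.** Weeks 2 to 31 contain 30 weekly injections. Alternating active and placebo makes 15 of them placebo in Arm 2. In Arm 3 every injection before Week 16 is placebo. Week 0 is the reference day for scheduling, so it cannot itself be off-window. That leaves 15 pre-crossover placebo injection visits (Weeks 1 to 15) that can.

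**Size.** The plan states no off-window rate and no expected PK retention, so there is no figure to reproduce. Let p be an assumed probability, independent across visits, that an injection is off-window, and let m be the number of post-baseline injection visits that count up to and including the sampling visit.

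- Share kept = (1 − p)^m. As written, m = 12 at Week 12, 24 at Week 24 and 31 at Week 32 (the last injection is at Week 31).
- If only bermekimab injections counted, m = 16 at Week 32 in Arm 2 (Week 1 plus 15) and in Arm 3 (Weeks 16 to 31). In Arm 1 m stays at 31.
- Arm 3 loss from placebo injections alone = 1 − (1 − p)^15.

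| p | Week 12, as written | Week 24, as written | Week 32, as written | Week 32, bermekimab only (Arms 2 and 3) | Arm 3 lost through Weeks 1–15 placebo |
|---|---|---|---|---|---|
| 0.5% | 94% | 89% | 86% | 92% | 7% |
| 1% | 89% | 79% | 73% | 85% | 14% |
| 2% | 78% | 62% | 53% | 72% | 26% |
| 5% | 54% | 29% | 20% | 44% | 54% |

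About 150 patients randomized 1:1:1 is about 50 per arm. At Week 32 the rule as written then keeps about 42.8, 36.6, 26.7 and 10.2 participants per arm at the four rates. Counting only bermekimab injections in Arms 2 and 3 keeps 46.1, 42.6, 36.2 and 22.0.

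**Effect of independence.** If lateness clusters within participants, more are kept at the same average rate. As an illustration, let 10% of participants have a 30% rate and 90% a 2.2% rate. The average is 0.1 × 30% + 0.9 × 2.2% = 4.98%, about 5%. Week 32 retention is 0.1 × 0.70^31 + 0.9 × 0.978^31, about 45%, against 20% under a common 5% rate.

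**Assignment rules.** The bullet in 7.1.1.1 comes under this lead-in: "Unless otherwise specified, the following data handling rules will apply to PK analyses". If that clause made the bullet yield to 7.1, the bullet would have no effect. If the bullet governs, the sentence in 7.1 has none. One of the two must go.

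**The case against.** The strongest reply is that the intent is clear from context. The rule sits under a heading on bermekimab concentrations, follows criteria that mostly name bermekimab, and serves an analysis set that begins at the first bermekimab dose. On that view a late placebo injection was never meant to count. This may well be the intent, but the text does not say it, and a programmer working from the text could implement the opposite.

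It is also fair that restricting by-visit summaries to participants dosed on schedule is a coherent choice. With weekly visits and a 3-day window, an off-window bermekimab injection is at least 4 days from its scheduled day, a real departure from the regimen. That stands, and it is why the restriction itself need not be removed for bermekimab doses. Early samples also lose less: at an assumed 2%, about 90% remain at Week 5 and 85% at Week 8.

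A reader might infer several stronger points that the documents do not support:

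- **Samples are thrown away, or Arm 3 participants lose all their PK data.** The text says the data "will be excluded from the by-visit data analyses". It does not remove them from the optional population PK or exposure-response work, and exclusions must be documented in the study report.
- **The percentages are forecasts.** They rest on assumed rates.
- **By-visit exposure is biased in a known direction.** The retained group is selected on dosing history, but nothing in the documents links that history to concentration.
- **The assignment conflict adds to the shrinkage.** It does not. Its numerical effect is small, because anyone given an incorrect agent or dose already leaves the by-visit analyses from that point.

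**Conclusion.** The point holds as a defect of wording with a potentially material effect on descriptive PK summaries. As written, the window rule is permanent and not limited to bermekimab, so placebo timing can remove valid concentrations in Arms 2 and 3. The two assignment rules contradict each other.

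The size cannot be fixed from the documents. Across assumed independent rates of 0.5% to 5%, Week 32 by-visit retention runs from 86% down to 20%, and Arm 3 loss from placebo injections alone runs from about 7% to 54%. These figures ignore dropout and the other exclusion criteria; clustering of lateness would raise retention. The primary efficacy analysis and the sample size are not affected. The changes should be made because they are nearly free and prevent a needless loss of data.

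**What to change.** 1. In SAP 7.1.1.1, insert the word bermekimab before administration in the window rule, so that only active injections trigger it. The skipped-dose criterion already names bermekimab and needs no change.
2. Beside the restricted by-visit summary, add a sensitivity summary that keeps all samples from treated participants. This matters most for Arm 1, where every injection is active and change 1 recovers nothing.
3. Reconcile SAP 7.1 and 7.1.1.1 to a single treatment-assignment rule for PK.

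The cost is a few words of SAP text and one extra table, whose means will mix more varied dosing histories. Trial conduct and data collection do not change. A rule letting participants back in after a set number of on-schedule doses is not required: it is a debatable choice and would need half-life data that the documents do not give.

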## 7.1.2. PK vs Efficacy

The relationship between bermekimab concentrations and efficacy endpoints may be explored, e.g.:

• The relationship between bermekimab concentrations (quartiles) and proportion of participants achieving HiSCR and change from baseline in AN count.

## 7.1.3. Population PK Analysis

When appropriate, population PK analysis may be performed using bermekimab concentrationtime data with the nonlinear mixed-effects modeling (NONMEM) approach. Details will be provided in a separate technical report.

#### 7.2. Immunogenicity

Immunogenicity analyses will be based on the Immunogenicity Analysis Set (Section 2.4.5). Participants will be analyzed according to the randomized treatment groups they were assigned to, regardless of the treatments they actually received. No imputation for missing concentration data will be performed.

Immunogenicity data through Week 36 will be summarized by treatment groups including

- Placebo  $\rightarrow$  Bermekimab 400 mg qw
- Bermekimab 400 mg q2w
- Bermekimab 400 mg qw
- Combined Bermekimab

## 7.2.1. Antibodies to Bermekimab

Blood samples will be collected to examine the formation of antibodies to bermekimab at the specified visits as shown in the schedule of activities in the protocol. Samples will also be collected at the final visit from participants who terminate study participation early.

The antibodies to bermekimab status (positive, negative) and titers will be summarized by treatment group for participants who receive at least one dose of bermekimab and have appropriate samples for detection of antibodies to bermekimab. The maximum titers of antibodies to bermekimab will be provided for participants who are positive for antibodies to bermekimab.

A listing of participants who are positive for antibodies to bermekimab will be provided. This listing will provide information regarding dose administered, bermekimab concentration, and antibody status for all visits.

## 7.2.2. Antibody vs PK/Efficacy/Safety

To explore the relationship between antibodies to bermekimab status and serum bermekimab concentrations, efficacy and safety, the following analysis may be performed if sufficient numbers of participants are positive for antibodies:

- Summary of bermekimab concentrations by antibodies to bermekimab status.
- Plots of mean (SD) trough bermekimab concentrations over time by antibodies to bermekimab status.
- Summary of clinical response status (e.g., proportion of participants achieving HiSCR and change from baseline in AN count) by antibodies to bermekimab status.
- Summary of injection-site reactions by antibodies to bermekimab status if applicable.
- List of antibodies to bermekimab status in participants who discontinued study early.

#### 7.3. Biomarkers

Biomarker assessments will include the evaluation of relevant markers in serum for all participants. The samples will be used to better understand the biology of HS in some or all of the following ways: to provide mechanistic assessment of the pharmacodynamic response of participants to treatment with bermekimab, to analyze differences between responders and nonresponders, and to determine if the markers might be used to classify participants as potential responders prior to treatment.

Serum samples will be analyzed for circulating factors such as cytokines and other inflammatory markers (eg, IL-17A, IL-17F, IL-23, TNF $\alpha$ , IL-6, IL-22), and other categories of biomarkers potentially associated with the development and progression of HS or related to the bermekimab mechanism of action. These analyses are considered exploratory and will be summarized in a separate biomarker technical report.

